## **2. Secondary End Points:**

To compare the side-effects, including weight gain, irregular vaginal bleeding, breast pain, appetite changes, nausea, vomiting, rash, jaundice, thromboembolism, hypertension, liver dysfunction, kidney dysfunction, glucose intolerance, and diabetes.

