**2.3 Conditions for Withdrawal from the Treatment (meeting any one of the following conditions)**

- (1) The participants volunteer to withdraw from the trial;
- (2) If the participants have PD on the histologic diagnosis; if the participants have PR and NC after 6 to 9 months of progestogen-based therapy; and if the participants have recurrence of disease while preparing for or during pregnancy;
- (3) If the participants cannot tolerate adverse drug reaction and are judged unfit for medical treatment by the clinician-in-charge.

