**3. Study Design**

**3.1 For Patients Having EAH**

The treatment schedule for EAH is summarized in Figure 1 and Table 1.

**Fig. 1** Study design. EAH, atypical endometrial hyperplasia; EC, endometrial cancer; MPA, medroxyprogesterone acetate; QD, once a day; LNG-IUS, Levonorgestrel-Releasing intrauterine system, Mirena®, Bayer Health Care Pharmaceutical Inc., Wayne, NY; GnRH-a, gonadotropin-releasing hormone agonists, Leuporelin acetate microspheres; mo, months; CR, complete response; PR, partial response; NC, no change; PD, progressive disease

**Table 1** The treatment schedule for atypical endometrial hyperplasia

Visits	1st	2nd	3rd	4th	5th	6th	7th	8th	9th	10th	11th	12th
Times	-1	-1/4	0	1	2	3	4	5	6	7	8	9

(month)												
Procedures	Pre-screening	Screening	Treatment Beginning	The 1st cycle			The 2nd cycle			The 3rd cycle (if necessary)		
History collection	√					√			√			√
Physical examination	√	√	√			√			√			√
Weight	√		√	√	√	√	√	√	√	√	√	√
Thinprep cytology test (TCT)	√											
Breast ultrasound	√											
Gynecological ultrasound	√					√			√			√
Endocrine examinations	√											
Liver function test	√			√	√	√	√	√	√	√	√	√
Coagulation function test	√					√			√			√
Pathology examinations	√	√				√			√			√
Hysteroscopy		√				√			√			√
Criteria	√	√				√			√			
Informed consent			√									
Random assignment			√									
Medical treatment			√	√	√	√	√	√	√	√	√	
Response evaluation						√			√			√
Adverse resection				√	√	√	√	√	√	√	√	√
Adverse events			√	√	√	√	√	√	√	√	√	√

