**Comments:**

(1) The basic history collection includes detailed history of prior treatment; with or without contraindications of oral highly active progestogens: hypertension, diabetes (DM), liver function damage, thrombotic disease and so on; with or without reproductive endocrine disease: infertility, PCO syndrome, insulin resistance (IR), impaired fasting glucose (IFG) and so on; with or without any other system disease; surgical history, allergy history; family history especially for carcinomas.

(2) The basic endocrine examinations include sex hormone, anti mullerian hormone (AMH), and insulin release test (IRT) to rule out PCO syndrome, IR, IFG, and DM. Follow-up treatment will be provided when necessary.

(3) If the patients have abnormality in breast ultrasound, she needs to visit the Department of Breast Surgery to evaluate the risk of continuous progesterone treatment.

(4) Based on the inclusion and exclusion criteria of this study, the patients are allocated to one of the arms by central randomization with study site allocation. The arms and interventions and the probability of distribution are as follows:

1) If the patients does not have thromboembolism, liver dysfunction, hypertension, or diabetes, she will be assigned to one of the following two groups, with a probability of 50%, respectively: a) sequential oral medroxyprogesterone acetate (MPA) 500mg QD group; and b) LNG-IUS (Mirena®) group.

2) If the patients are diagnosed of thromboembolism, liver dysfunction, hypertension, or diabetes, she will be assigned to one of the following two groups, with a probability of 50%, respectively: a) intramuscular injection of leuporelin acetate microspheres (GnRH-a) + LNG-IUS group; and b) LNG-IUS (Mirena®) group.

(5) For the groups of oral highly active progestogens, medicine treatment should only be continued if the liver function is normal, which is evaluated by monthly tests.

(6) For the groups of LNG-IUS, the medical device needs to be replaced by a new one on every hysteroscopy to insure adequate drug release

(7) Endometrial tissue sampling for diagnosis should be performed by hysteroscopy every 3 months, and the histologic diagnoses of all specimens are made by two categorized pathologists.

[figure not shown]

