(8) After 6 months' continuous progestogen-based therapy, if the patients has PR/NC, progestogen-based therapy should be continued for one more cycle (3 months), and if the patient still has PR/NC, she will withdraw from this trial and undergo hysterectomy; if the patients has CR at the second or third endometrial evaluation, fertility treatment will be initiated immediately; and if the patients has documented progression on the biopsies at any time, the protocol treatment will be stopped and hysterectomy be recommended.

(9) The option of natural conception or assisted reproduction should be discussed with the fertility specialist in the reproduction center of our hospital; assisted reproduction is recommended if the patients 1) has history of infertility; 2) has risk factors for infertility such as PCO syndrome, obesity, diabetes, and lack of ovulation; or 3) suffers from failed pregnancies after 6 months of natural conception.

- (10) If the patient succeeds in conceiving, she will receive professional prenatal examinations from the obstetrics specialist in our hospital.
- (11) All the professors in the Department of Obstetrics and Reproductive Center of our hospital are on this research team.
- (12) Long-term follow-up will proceed even after treatments are finished, and corresponding clinical treatments will be provided for patients with different conditions.

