**Comments:**

(1) The basic history collection includes detailed history of prior treatment; with or without contraindications of oral highly active progestogens: hypertension, diabetes (DM), liver function damage, thrombotic disease and so on; with or without reproductive endocrine disease: infertility, PCO syndrome, insulin resistance (IR), impaired fasting glucose (IFG) and so on; with or without any other system disease; surgical history, allergy history; family history especially for carcinomas.

(2) If the patient is suspected of having LS, endometrial samples should be taken for pathological immunohistochemistry, and genetic test should be done when necessary.

(3) The basic endocrine examinations include sex hormone, anti mullerian hormone (AMH), and insulin release test (IRT) to rule out PCO syndrome, IR, IFG, and DM. Follow-up treatment will be provided when necessary.

(4) Disease limited to the endometrium (stage 1A) on MRI is confirmed by the designated radiologists.

(5) Laparoscopic multipoint biopsy of ovary and peritoneum when CA 125/199 or imaging examinations are remarkable, so as to rule out ovarian tumor or other metastases.

(6) If the patients has abnormality in breast ultrasound, she needs to visit the Department of Breast Surgery to evaluate the risk of continuous progestogen treatment.

(7) Based on the inclusion and exclusion criteria of this study, patients will be allocated to one of the arms by central randomization with study site

allocation. The arms and interventions and the probability of distribution are as follows:

1) If the patient does not have thromboembolism, liver dysfunction, hypertension, or diabetes, she will be assigned to one of the following three groups, with a probability of 33%, respectively: a) sequential oral medroxyprogesterone acetate (MPA) 500mg QD group; b) sequential oral medroxyprogesterone acetate (MPA) 250mg QD + LNG-IUS (Mirena®) group; and c) LNG-IUS (Mirena®) group;

2) If the patient is diagnosed of thromboembolism, liver dysfunction, hypertension, or diabetes, she will be assigned to one of the following two groups, with a probability of 50%, respectively: a) intramuscular injection of leuprorelin acetate microspheres (GnRH-a) + LNG-IUS group; and b) LNG-IUS (Mirena®) group.

(8) For the groups of oral highly active progestogens, medicine treatment should only be continued if the liver function is normal, which is evaluated by monthly tests.

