#### **3. Statistics:**

SPSS software will be used for statistical analysis. Survival analysis is used for primary end points and chi-square test for secondary end points.

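### Weight gain has only a chi-square test and no stated amount, reference weight or visit; analyse monthly weight as change from month 0 to month 6, with a predefined proportion as support.

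*Combined protocol and SAP*

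**What the plan says.** The whole analysis text is III.3 Statistics. It names SPSS, survival analysis for the primary end points, and "chi-square test for secondary end points", without exception. I.2 Secondary End Points reads "To compare the side-effects, including weight gain" and goes on to list 13 further side-effects, most of them present-or-absent events.

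Tables 1 (EAH) and 2 (EC) schedule weight at month -1, month 0 and every month from 1 to 9. There are thus two pre-treatment weights and up to nine on treatment. Months 7 to 9 are headed "The 3rd cycle (if necessary". Section 3.1 comment (8) says "if the patients has CR at the second or third endometrial evaluation, fertility treatment will be initiated immediately", so only women with PR or NC at month 6 go on to the third cycle. The EC text in 3.2 comment (11) matches.

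Treatment may also end before month 6:
- for progression: "if the patients has documented progression on the biopsies at any time, the protocol treatment will be stopped" (3.1 comment (8));
- for intolerance: "If the participants cannot tolerate adverse drug reaction and are judged unfit for medical treatment" (2.3);
- in the groups taking oral progestogen only: "medicine treatment should only be continued if the liver function is normal" (3.1 comment (5); 3.2 comment (8)).

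Oral progestogen is randomised against LNG-IUS only in women without contraindications. In EC, "she will be assigned to one of the following three groups" (3.2 comment (7)), with 18 women per arm; in EAH there are two arms of 20 (III.1). No section defines weight gain by amount, reference weight or visit.

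**The concern.** A chi-square test needs a category. To turn up to eleven scheduled weights per woman into yes or no, someone must choose an amount, one of two reference weights, and a visit or window. If those choices are made after the data are seen, they can change the result.

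The visit matters most. Weights at months 7 to 9 exist on treatment only for women who had not reached CR by month 6. A month-9 or any-visit definition would therefore give women different lengths of observation according to response.

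Even with the event defined, a woman just over the threshold counts the same as one far over it. In arms of 18 or 20 that usually costs power. The comparison matters to the trial's rationale, because section V cites milder systemic effects, weight gain among them, as an advantage of LNG-IUS over oral progestogens.

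**Working it through.** The plan gives no mean, SD, rate or threshold for weight, so there is no figure of its own to reproduce. The arm sizes (18 and 20) and alpha 0.05 come from III.1. Two-sided testing and every kg value below are assumptions.

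**1. Information kept by a two-category cut (normal outcome, no kg assumption).** Efficiency = φ(c)² / [p(1 − p)], where p is the proportion above the cut c.
- p = 0.5: 0.3989² / 0.25 = 0.637
- p = 0.2: 0.2800² / 0.16 = 0.490
- p = 0.1: 0.1755² / 0.09 = 0.342

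**2. Power for one pair of arms.** Assume mean gains of 1 and 4 kg and SD 4 kg, so d = 3/4 = 0.75. The t-test noncentrality is d√(n/2): 2.25 at n = 18 and 2.37 at n = 20. The proportions above 2.5 kg are 1 − Φ(0.375) = 0.354 and 1 − Φ(−0.375) = 0.646. Above 5 kg they are 1 − Φ(1) = 0.159 and 1 − Φ(0.25) = 0.401. Chi-square power is by exact binomial enumeration, without continuity correction.

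| n per arm | continuous | chi-square, 2.5 kg | chi-square, 5 kg |
|---|---|---|---|
| 18 | 0.589 | 0.474 | 0.366 |
| 20 | 0.637 | 0.433 | 0.416 |

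The fall from 0.474 to 0.433 as n rises is discreteness: the actual test size at that cut is 6.5% at 18 and 4.3% at 20. The normal approximation gives 0.41 and 0.36 at 18 per arm, and 0.45 and 0.40 at 20.

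**3. Range.** Over differences of 2, 3 and 4 kg, SDs of 3 to 6 kg and both cuts (24 combinations), the loss of power is 0.01 to 0.31 (median 0.12) at 18 per arm and 0.05 to 0.29 (median 0.17) at 20. For the overall three-arm EC comparison (F-test against 3×2 chi-square, 18 per arm, SD 4 kg, three patterns of means) it is 0.17 to 0.26.

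**4. Other distributions (18 per arm, same means and SD; t-test against chi-square at 2.5 and 5 kg).**
- Right-skewed, gamma shape 2: 0.605 against 0.456 and 0.222
- Heavy-tailed, t with 5 df: 0.617 against 0.626 and 0.417
- Laplace: 0.612 against 0.764 and 0.367

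**5. Leaving the definition open.** This is a simulation with no true difference, 20 per arm and an assumed growth pattern. One fixed definition gave 4% false positives. Taking the most favourable of 24 (two baselines × months 3, 6, 9 × four cut-offs) gave about 37%. Every simulated woman had a month-9 weight, so this shows the mechanism and does not forecast this trial.

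**6. Early stops.** Assume a true month-6 difference of 3.0 kg, month-3 to month-6 correlation 0.65, and 4 of 18 oral and 1 of 18 LNG-IUS women stopping. Women still on treatment at month 6 then show:
- 2.3 kg if the stoppers are exactly those with the largest month-3 gains;
- about 2.8 kg if stopping correlates 0.3 with that gain;
- 3.0 kg if stopping is unrelated to it.

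**7. Small counts.** With equal arms, an expected count of 5 needs a pooled rate of 5/n: 36% at 14 per arm, 28% at 18, 25% at 20 and 17% at 30.

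**The case against.** The best case for the plan is that weight gain stands in a list of side-effects beside rash and nausea, and both tables have an adverse-event row at each treatment visit. It can be recorded there as yes or no, and chi-square suits a comparison of incidence. On that view one sentence defining the event is enough, and a mixed model merely swaps the proportion for a mean.

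Much of this stands. A reader might infer that measured weight has to be dichotomised, or that chi-square is invalid here; the documents support neither. But a clinician's yes or no also needs a criterion, and none is given. The proportion is a legitimate measure, so it should be kept; it need not be the only use made of monthly weights.

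A reader might also infer that differential stopping, through the liver-function rule for oral treatment, will bias the comparison. That is not shown. No stopping rule is based on weight, nothing says that only completers are compared, and nothing says that weighing ends when a drug stops; follow-up continues after treatment (3.1 comment (12); 3.2 comment (15)). The 2.3 kg figure is an extreme case with invented stop counts.

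It is also fair that liver dysfunction, kidney dysfunction, hypertension and glucose intolerance rest on measurements without stated cut-offs. That is a separate gap, which this change does not close.

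**Conclusion.** The point holds as a recommended improvement. Chi-square is the only test named for an end point measured monthly, and the event it would compare has no amount, reference weight or visit. Those omissions rest on the text alone.

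The size of the power loss rests on assumption. At most 64% of the information is kept under normality. In the assumed base case power falls by 0.12 or 0.22 at 18 per arm (0.589 − 0.474; 0.589 − 0.366) and by 0.20 or 0.22 at 20 (0.637 − 0.433; 0.637 − 0.416). A reader might infer that categorising always loses power. It does not: with heavy tails a central cut can equal or beat the t-test. Nor would the continuous analysis make this comparison well powered, since power stays below 0.8 either way in the base case. Bias from early stops is a possibility only, from none to 0.7 kg in the scenarios shown.

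The consequence is confined to one of 14 listed secondary side-effects. The primary end points are untouched.

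**What to change.** In III.3, add text to this effect:
- **Main analysis.** Weight is analysed as change from month 0 to month 6 within each disease-by-contraindication stratum. A mixed model of change at months 1 to 6 includes arm, month, arm-by-month and month-0 weight, with unstructured covariance and Satterthwaite degrees of freedom. A named simpler covariance structure is used if the model does not converge. This matters because six visits need 6 × 7 / 2 = 21 covariance parameters and the smallest stratum has 14 women per arm. Report the adjusted mean difference at month 6 with 95% CI.
- **Three-arm EC stratum.** Each oral-containing arm is compared with LNG-IUS alone, reported as secondary with no multiplicity claim.
- **Early stops.** All recorded weights to month 6 are used, including any taken after treatment stops. Early stops are tabulated by arm and reason. ANCOVA at month 6 is a sensitivity analysis.
- **Supportive analysis.** The proportion gaining weight is compared by chi-square, or by Fisher's exact test when expected counts are small. Baseline is month 0 and the visit is month 6. One threshold is written into the SAP before any outcome data are seen; the documents give no basis for its value, so the investigators must supply it.
- Chi-square stays for side-effects that are naturally yes or no.

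The cost is SAP wording and one model per stratum in SPSS, which the plan already names; no visit or measurement is added. There are two drawbacks. The main weight result becomes a mean in kg and not a proportion. The model also assumes that missing weights depend only on arm and recorded weights.

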### **IV. The Principle of Ethics**

When data are entered, the real name of the participant will be replaced by a number, which is given in the order of admission. All information will be kept strictly confidential. When the research results are published, no personal data will appear, and the original data will be properly kept. Without the consent of the participant, no relevant information will be disclosed to anyone who is not involve in this study. The principal investigator (PI) will submit the relevant technical information to the ethics committee, and the research can only be conducted upon approval.

## **V. Research Status and Development Trend**

Endometrial carcinoma (EC) is the most common gynecology cancer worldwide, and is usually characterized by well-differentiated (grade 1 [G1]) and early stage (according to International Federation of Obstetrics and Gynecology [FIGO] staging system--stage IA), which contributed to a very high cure rate with standard treatment.[14, 15] Atypical endometrial hyperplasia (EAH) suggests a preliminary state with progression to EC, and tends to occur in young women. [1, 6-8] For these young patients, conventional treatment using hysterectomy affects their quality of life immensely because it deprives them of any chance to bear a child. If the patients have a strong wish to preserve their fertility, the fertility-preserving treatment can be considered. In China, as lifestyle and diet both change, the incidence of EC has been increasing very rapidly,[5, 14] and the need for fertility-preserving treatment is also on the rise.

The efficacy and safety of oral progestogens as fertility-preserving therapy in patients with EAH and EC has been reported in many studies. For instance, the first report was conducted by Kelley and Baker in 1961[16]. Oral progestogens function by inhibiting the estrogen receptor, leading to a decrease in endometrial cell mitosis, promotion of apoptosis, and production of secretory endometrium[17]. However, the highly active progestogens often have many and severe side-effects like gastrointestinal reaction, insomnia, nervousness, dizziness, coagulation, liver and

kidney dysfunction, and weight gain etc. In addition, these patients always have complications such as obesity, hypertension, and impaired glucose metabolism, which often make the patients withdraw from therapy. Therefore, an effective and safe conservative treatment is urgently needed for young patients having EAH and EC who wish to preserve their fertility but cannot tolerate the highly active progestogen treatment. It has become increasingly important and necessary to find a safe and effective fertility-preserving treatment with better tolerability, and fewer and milder side effects.

Clinically, Mirena® LNG-IUS is one of the most widely used Levonorgestrel-releasing intrauterine devices, which is produced by Bayer Health Care Pharmaceutical Inc., Wayne, NY. Mirena®, the progestogen device, has high contraceptive effectiveness. Each Mirena contains 52 mg of levonorgestrel. Its in vivo drug rate during the first five-year period is approximately 20 ug /day and will reduce to 11 ug/day in five years. The hormone released from the IUS causes significant local effect characterized by glandular atrophy and stromal decidualization. This dominant suppressive effect of the endometrium is seen through the overall thickness of the arterial walls with capillary thrombosis. The end result is that the suppression of endometrial tissue growth becomes insensitive to estradiol. The LNG-IUS has an important role in the disease prevention or treatment of uterine pathologies, such as endometrial polyps, endometrial cancer, and tamoxifen-induced changes[18]. Compared with oral progestogens, LNG-IUS can elevate the local drug concentration and act on the PgRs in the endometrium directly, which generates a much higher concentration of progesterone in the endometrial mucosa[17]. LNG-IUS may still be a useful treatment option, especially because it has fewer and milder systemic side-effects such as weight gain and liver damage[6]. Some studies suggest that LNG-IUS is superior to oral progestogens in the fertility-preserving treatment of EAH and EC. Gallos et al[19] reported in a systemic review that LNG-IUS achieved a higher pooled regression rate than oral progestogens for EAH (90 vs 69%,  $P = 0.03$ ).

A higher regression was also seen in a randomized, multicenter study carried out by Orbo et al[20]. This is similar to findings of some studies and systemic reviews[17, 21]

The use of LNG-IUS alone or in combination with GnRH-a, oral progestogens for fertility-perserving treatment of EC and EAH has been proposed in many guidelines[1, 3, 5, 7, 8, 11]. LNG-IUS was suggested as the first-line medicine treatment for patients having EAH by RCOG-BSGE[1]. In summary, (1) several recent studies have reported encouraging results on fertility-preserving treatment of EC and EAH. (2) Nevertheless, studies focusing on the efficacy and safety of LNG-IUS used alone are still insufficient and weak and based almost exclusively on small studies. (3) In addition, LNG-IUS is used by many only in conjunction with other medicines. Therefore, an appropriately designed RCT is needed urgently to evaluate different fertility-preserving treatments of EAH and EC.

